4.2 Efficacy Analysis

Efficacy will be evaluated in the FAS, with participants analysed according to their randomized treatment assignment. Analyses in the PPS will be performed as sensitivity assessments, and comprehensive listings of all efficacy end points will be provided.

For each efficacy end point, percent change from baseline will be calculated as

$$(\text{Baseline value} - \text{Post- baseline value}) \div \text{Baseline value} \times 100\%$$

4.2.1 Primary Efficacy Analysis

The primary end point—the percent change from baseline in the 24-hour mean PAC count at Week 6—will be evaluated with an analysis- of- covariance (ANCOVA) model. Treatment group will be included as a fixed effect, and age and baseline 24-hour mean PAC count will be included as covariates. The between- group effect will be reported as the least- squares mean difference with its two- sided 95% confidence interval (CI) and p value.

Least- squares mean percentage reductions in the 24-hour mean PAC count will be plotted for each scheduled visit to depict response trajectories in both treatment groups.

Missing-Data Handling

Missing values for the Week 6 primary end point will be addressed with multiple imputation.

- **Imputation Procedure** Twenty complete data sets will be generated separately within each treatment group with a Markov chain Monte Carlo (MCMC) algorithm (PROC MI, SAS; seed = 20240716).

- **Imputation Model Covariates** Age, baseline 24-hour mean PAC count, and the 24-hour mean PAC count at every post-baseline visit.

After imputation, the data sets from both treatment groups will be combined. Each imputed data set will be analyzed with the prespecified ANCOVA model for the primary end point. Results will be pooled according to Rubin's rules with PROC MIANALYZE (SAS) to yield the final least-squares mean treatment difference with its two-sided 95% CI and P value.

Sensitivity Analysis:

A mixed-effects model for repeated measures (MMRM) will be applied to the primary end point as a prespecified sensitivity analysis. The model will include treatment group, visit, and the treatment-by-visit interaction as fixed effects and age and the baseline 24-hour mean PAC count as covariates. Parameters will be estimated with restricted maximum likelihood, and denominator degrees of freedom will be determined with the Kenward–Roger approximation.

Within-participant variability will be modeled with an unstructured covariance matrix. If the model fails to converge, alternative covariance structures will be evaluated sequentially—heterogeneous Toeplitz, heterogeneous first-order autoregressive, heterogeneous compound symmetry, Toeplitz, first-order autoregressive, and compound symmetry—until convergence is achieved; the first structure that converges will be retained.

Results will be presented as the least-squares mean treatment difference with the corresponding two-sided 95% CI.

4.2.2 Secondary Efficacy Endpoint Analysis

All secondary efficacy end points will be evaluated in the FAS. Missing data for secondary end points will not be imputed.

- **Continuous Endpoints** At each scheduled visit, analyses will be based exclusively on observed values (observed-cases approach); participants lacking data at a given visit will be omitted from that visit's analysis.

- **Categorical Endpoints** Participants with missing data will be classified as non-responders—that is, as not having met the specified end point.

a) The change from baseline in the 24-hour mean number and burden of PACs at Weeks

4, 6, and 8;

- b) The change from baseline in the 24-hour mean episode count and burden of NSAT at Weeks 4, 6, and 8;
- c) The change from baseline in the 24-hour mean episode count of SAT, AF, and AFL at Weeks 4, 6, and 8;
- d) The proportion of participants with new-onset SAT, AF, or AFL lasting \geq 30 seconds during a continuous 72-hour monitoring period at Weeks 4, 6, and 8. This endpoint will be calculated based on the first occurrence of SAT, AF, or AFL during the respective 72-hour monitoring windows;
- e) The cumulative incidence of new-onset AF from baseline to Week 8: The proportion of participants who experience their first episode of AF lasting \geq 30 seconds during any of the 4th, 6th, or 8th-week follow-up windows, with each participant counted only once, even if they have multiple occurrences across different follow-up windows;
- f) The change from baseline in the SF-36 quality of life score at Week 6;
- g) The responder rate for PACs or NSAT will be calculated at Weeks 4, 6, and 8 and compared between the memantine and placebo groups. A PAC responder is defined as a participant whose 24-hour mean PAC count is reduced by \geq 50% from baseline after treatment, and an NSAT responder is defined as a participant whose 24-hour mean NSAT burden is reduced by \geq 50% from baseline after treatment.
 - For categorical end points, counts and proportions will be summarized by treatment group. Two-sided 95% CIs for incidence, cumulative incidence, or response rate will be calculated with the Clopper – Pearson method. The absolute risk reduction (ARR = incidence in the memantine group – incidence in the placebo group) will be reported, and between-group differences will be tested with a stratified Cochran – Mantel – Haenszel χ^2 test that uses the randomization strata—age (\geq 65 vs. $<$ 65 yr) and baseline PAC count (\geq 5000 vs. $<$ 5000 beats/24 h)—as stratification factors. The relative risk (RR = incidence in the memantine group \div incidence in the placebo group) and its 95% CI, together with the number needed to treat (NNT = $1/|ARR|$), will also be presented.
 - For continuous end points—including the change from baseline at weeks 4, 6, and 8 in the 24-hour mean PAC count and burden; the episode count and burden of NSAT; the

episode count of SAT, AF, and AFL; and the change from baseline to week 6 in the total SF-36 score—an ANCOVA will be fitted. The model will include treatment group as a fixed effect and age and the baseline value of the respective end point as covariates. For each end point, the least-squares mean difference between groups, its two-sided 95% CI, and the corresponding p value will be reported.

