4.3.2 Investigator-Initiated Withdrawal

4.3.2.1 Discontinuation of Study Drug

The investigator may discontinue study treatment for safety or other compelling reasons, including:

- (1) Medical or ethical considerations that, in the investigator's judgement, necessitate cessation of treatment.
- (2) Allergic reactions, neuropsychiatric symptoms, or any other SAE requiring discontinuation.
- (3) An emergent clinical condition mandating alternative therapy.
- (4) Any unforeseen circumstance that, in the investigator's judgement, warrants early termination of treatment.

Participants who discontinue study drug for any of the above reasons must complete the early-termination visit and continue follow-up as outlined in the protocol (on-site or by telephone).

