6.1 Study Flow Diagram

	Screening period ¹ (≤14d)	treatment period			follow-up period	early withdrawal Visits ²	Symptom initiation additional visit
manipulate	V1	V2	V3	V4	V5		
		D7±2d	D28±3d	D42±3d	D56±3d	Day of exit +7d	
Signed informed consent							
Symptom assessment ³							
Inclusion/exclusion criteria							
Demographic information							
Basic information ⁴							
Prior and co-morbidities, smoking and drinking, history of allergies ⁵							
History of prior non-drug treatment, prior drug therapies ⁶							
Vital signs ⁷							
NYHA Cardiac Function Classification							

Cardiac ultrasound							
Hematology tests ⁸							
Urine PH							
Blood or urine HCG ⁹							
12-lead ECG							
3-day cardiac patch monitoring ¹⁰							
Randomization	 (D0)						

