Issuance and collection of diary cards	 (Issuance only)					 (Collection)	
Return of experimental drugs						 (If applicable)	
Adjustment of medication							
AEs and co-medication							
SF-36 Health Questionnaire Scores							

Table 4 Study Flow Diagram

Notes:

1. The screening period examination of this study can accept the relevant examination results of our center or the local tertiary hospital within 1 month prior to the informed date (acceptable at the judgment of the investigator, otherwise the relevant examination is required).
2. If a subject withdraws from the study after completing the end - of - treatment visit (V4), for the relevant examinations related to early withdrawal (excluding the 3 - day ECG patch monitoring), if the time interval from the V4 visit is \leq 7 days or the investigator determines that repetition is unnecessary, these examinations do not need to be repeated. However, the reason for not conducting

the examinations should be described in the original case report. Pregnancy tests should be carried out as required. If a subject withdraws before V4, regardless of whether the V3 visit has been completed, all relevant procedures for early withdrawal must be performed.

3. Symptom assessment: the assessment includes the nature of the PACs symptoms, the frequency and duration of the episodes, and whether the nature of the symptoms has changed.

Nature of symptoms: Palpitations, a fluttering or pounding sensation in the heart, a sense of the heart skipping beats, fatigue, weakness, shortness of breath, discomfort in the chest or precordial area, dizziness, etc.

Frequency of episodes: daily, weekly, monthly, etc;

Duration: minutes, hours, sustained;

Symptom scores:

Score 0: No symptoms;

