7.3.9 Handling of Missing Data

Primary Endpoint. Missing Week 6 24-hour PAC counts will be imputed by a prespecified multiple-imputation procedure, as detailed in the SAP.

Sensitivity Analyses. Robustness analyses for the imputation model will be described in the SAP.

Secondary Efficacy and Safety Endpoints. No imputation is planned; analyses will be performed on observed data only.

8. Safety Evaluation

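### SAP 4.2.2 counts a missing 72-hour recording as arrhythmia-free in the new-onset AF and SAT/AF/AFL end points, which understates incidence and favours whichever arm loses more recordings

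*SAP*

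**What the plan says.** SAP 4.2.2 opens its missing-data text with "Missing data for secondary end points will not be imputed". For categorical end points it then assigns a value: "Participants with missing data will be classified as non-responders—that is, as not having met the specified end point". No exception follows. The same section places event rates and response rates in one class: "Two-sided 95% CIs for incidence, cumulative incidence, or response rate will be calculated". The rule therefore covers end point d (new-onset SAT, AF or AFL by window), end point e (cumulative new-onset AF) and steps c to f of the testing hierarchy in SAP 2.4, all of which are AF end points.

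Protocol 7.3.9 says of secondary end points: "No imputation is planned; analyses will be performed on observed data only". Protocol 7.3.2 gives the SAP precedence where the two differ. SAP section 6 lists no deviation from the protocol.

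The protocol limits the loss of recordings. The schedule in 6.1 includes "3-day cardiac patch monitoring" at the early-withdrawal visit, and note 2 adds: "If a subject withdraws before V4, regardless of whether the V3 visit has been completed, all relevant procedures for early withdrawal must be performed". Under 4.3.2.1, participants taken off drug "must complete the early-termination visit and continue follow-up as outlined in the protocol". However, end point e counts AF only "during any of the 4th, 6th, or 8th-week follow-up windows", and the SAP does not say whether, or in which window, an exit recording counts.

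**The concern.** Scoring missing as not met is conservative when meeting the end point is the good result, as with a 50% fall in PACs. New-onset arrhythmia is the opposite case: not meeting the end point is the good result, so each lost recording lowers the arm's event count while the participant stays in the denominator.

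This has two consequences. Incidence is understated in both arms. If the arms lose recordings at different rates, the relative risk, absolute difference, NNT and CMH test move toward the arm that loses more, whichever it is. Four of the six key secondary tests are affected, and no missing-data sensitivity analysis is specified for them. The MMRM covers only the primary end point, and a per-protocol analysis would apply the same rule.

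**Working it through.** **Inputs from the documents.** 128 per arm; 15% overall dropout, not split by arm (protocol 7.1, SAP 1.3.2); visits at days 28, 42 and 56; two-sided 0.05 for each step (SAP 2.4). The plan gives no figure for AF. Its one related figure, power above 95% for the primary comparison, reproduces: 128 × 0.85 = 108.8 per arm, and a 20-point difference with SD 35 gives 98.7% at 108 per arm.

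**Assumptions, not in the documents.** True AF incidence p; the split of missingness between arms; missing share rising linearly, m_w = m × day/56 (so 0.5m, 0.75m and m); first AF equally likely in each window; missingness unrelated to AF. Splits are written memantine/placebo.

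**Reported incidence under the SAP rule.**
- Single window: p(1 − m_w). Week 8, p = 10%, m = 15%: 0.10 × 0.85 = 8.5%.
- Cumulative: (p/3) × Σ(1 − m_w) = p(1 − 0.75m). For p = 10%, m = 15%: 0.10 × 0.8875 = 8.9%.

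**Equal missingness, 15% in both arms.** The relative risk is unchanged and the null test stays valid. A true 10% versus 5% is reported as 8.875% − 4.4375% = 4.4 points instead of 5, so NNT is 22.5 instead of 20.

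**Unequal missingness, no true effect, cumulative AF.** RR = (1 − 0.75m_mem)/(1 − 0.75m_plac):
- 20%/10%: 0.850/0.925 = 0.92
- 25%/5%: 0.8125/0.9625 = 0.84
- 10%/20%: 0.925/0.850 = 1.09

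For the Week 8 window alone the ratio is (1 − m_mem)/(1 − m_plac): 0.80/0.90 = 0.89 and 0.75/0.95 = 0.79 for the first two splits.

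**Type I error at step c.** Exact binomial enumeration, 128 per arm, Mantel-Haenszel chi-square without the randomization strata, critical value 1.96, not conditional on earlier steps:

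| Split | True AF | Favours memantine | Favours placebo | Two-sided |
|---|---|---|---|---|
| 20%/10% | 5% | 3.2% | 1.6% | 4.8% |
| 20%/10% | 10% | 4.0% | 1.5% | 5.5% |
| 20%/10% | 15% | 4.4% | 1.3% | 5.6% |
| 25%/5% | 5% | 4.4% | 1.1% | 5.5% |
| 25%/5% | 10% | 6.2% | 0.9% | 7.0% |
| 25%/5% | 15% | 7.4% | 0.6% | 8.0% |

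At moderate imbalance the total barely moves. The damage is in its direction.

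**If every leaver has an exit recording and it counts in the next window.** Missing shares become 0, 0.5m and 0.75m, so RR = (3 − 1.25m_mem)/(3 − 1.25m_plac): 2.75/2.875 = 0.96 at 20%/10% and 2.6875/2.9375 = 0.91 at 25%/5%. The bias is roughly halved. Two-sided error at 20%/10% is 4.7%, 5.2% and 5.1% for AF 5%, 10% and 15%.

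**Life-table alternative.** With CMH over the three windows and 100,000 simulated trials per scenario, RR is 1.00 at both 20%/10% and 25%/5%, each tail is 2.2% to 2.6%, and two-sided error is 4.7% to 5.0% for AF 5% to 15%. With AF 5% versus 15% and 15% missing in both arms (40,000 trials), power is 73.1%, against 72.8% under the SAP rule.

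**If missingness depends on AF.** Take one window, AF 10%, 15% missing, AF cases twice as likely to be missing. The missing rate without AF is 0.15/(0.9 + 2 × 0.1) = 13.6%. Observed AF is 0.10 × (1 − 0.273) = 7.3% of all participants (SAP rule) or 7.3/0.85 = 8.6% of those observed. Both are below 10%, so observed data alone do not settle the matter.

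**The case against.** **The gate offsets the error.** Step c is reached only after the primary and steps a and b succeed, and step a uses the same missing rule, there against the arm that loses more. Take the plan's design values (50% versus 30%, SD 35%), normal responses, steps a and c independent, and the primary and step b always passed. Step a power is then 90% at 15%/15%, 79% at 20%/10% and 62% at 25%/5%. The chance of reaching step c and falsely rejecting falls to 0.79 × 4.8% to 5.6%, or 3.8% to 4.4%, at 20%/10%, and to 3.4% to 5.0% at 25%/5%. This stands, and it weakens the case about confirmatory error. It does not help if placebo loses more: at 10%/20% step a power is 96%, and with AF 10% the figure is 0.96 × 5.5% = 5.3%, with the excess now against memantine. A larger true PAC effect would also weaken the offset.

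**AF may be rarer than 5%.** Recent or baseline AF, AFL and SAT are excluded, and detection rests on three 72-hour windows. At 20%/10% and AF 1%, 2% and 3%, two-sided error is 1.8%, 4.4% and 4.6%, all below nominal. This also stands. However, neither the gate nor a low rate changes the reported ratio: RR is 0.92 at every AF rate, and these estimates are reported whether or not the gate opens.

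**The protocol already limits the loss.** Follow-up continues after drug is stopped, AF in an earlier window still counts cumulatively, and an exit patch is scheduled. All true. Even so, recordings can be lost through telephone-only follow-up or refusal (protocol 4.4), and the SAP gives the exit recording no place.

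**The precedence clause settles the conflict.** It settles which text governs. It does not make the rule suitable for a harmful event.

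**A life-table goes beyond the fault.** Partly fair. End point e is defined as a simple proportion, and an observed-data rule with the same sensitivity analyses would mend the core fault. It would still have to say how an AF-free participant with a missed window is counted.

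**Conclusion.** The concern holds. As written, the rule scores missing recordings as arrhythmia-free in end points d and e and in four of the six key secondary tests. It conflicts with protocol 7.3.9 and with the SAP's own no-imputation sentence.

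The understatement occurs whenever some unrecorded participants would have had an event. The between-arm bias needs unequal loss, and its direction follows the arm that loses more. Its size is illustrative, because AF rates, arm splits, the timing of loss and the spread of AF over windows are all assumed. On those assumptions the null RR for cumulative AF is 0.92 at 20%/10% and 0.84 at the more extreme 25%/5%; counting exit recordings would roughly halve the shift.

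The main harm is directional bias in the reported AF effect. Inflation of the confirmatory error is small once the gate is considered. The primary end point is unaffected. This should be fixed but is not critical.

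**What to change.** In SAP 4.2.2:

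1. Limit the missing-as-not-met rule to the PAC and NSAT responder end points.
2. For end point d and the Week 4, 6 and 8 AF tests, analyse FAS participants with an evaluable recording in that window, define evaluable in recorded hours, and keep the stratified CMH test.
3. For cumulative AF, use a discrete-time life-table over the three windows. An AF-free participant is at risk in each window with an evaluable recording and is censored after the last. Test with CMH, adding window to the randomization strata. Take RR, absolute difference and NNT from the life-table incidences, with life-table variances in place of Clopper-Pearson. State how a window missed between two evaluable ones is handled.
4. Assign the early-withdrawal recording to a window, for example the next scheduled one and only if that window has no scheduled recording. Participants who stop drug but stay in follow-up then get no extra chance of AF detection.
5. Add two sensitivity analyses: missing counted as an event, as an outer bound, and a tipping point by arm.

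Listing the retained responder rule in SAP section 6 as a departure from protocol 7.3.9 is housekeeping.

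The cost is SAP wording, a changed method for cumulative AF and one extra table. At 15% dropout with linear loss, single-window denominators fall to about 118, 114 and 109 of 128 per arm. Cumulative AF loses no material power in the scenario tested. The change should be fixed before unblinding; if that has passed, the revised analysis should be reported as a labelled sensitivity analysis.

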4.1 Inclusion Criteria

(1) Age: 18 to 80 years, inclusive.

(2) Symptomatic PACs: Documented at screening as $\geq 1,000$ PACs during a 24-hour ambulatory ECG recording.

(3) Informed consent: Ability and willingness to understand and comply with all study procedures and to sign the written informed-consent form before any protocol-specific activities are performed.

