4.2 Exclusion Criteria

(1) Atrial or ventricular arrhythmias

AF, AFL, or SAT documented by 12-lead ECG within 6 months before screening or detected on the baseline 72-hour patch-type ambulatory ECG;

Ventricular tachycardia (excluding brief nocturnal runs) or ventricular fibrillation.

(2) Recent cerebrovascular or cardiac events

Ischemic or hemorrhagic stroke, or transient ischemic attack, within 6 months before screening;

Cardiac surgery, myocardial infarction, percutaneous coronary intervention, or catheter ablation for atrial arrhythmias within 3 months before screening.

(3) Severe cardiac dysfunction

Left-ventricular ejection fraction $\leq 40\%$;

New York Heart Association class III or IV heart failure.

(4) Clinically significant conduction disease

Sick-sinus syndrome without a permanent pacemaker.

Second-degree type II or higher atrioventricular block, or bifascicular block.

(5) Recent antiarrhythmic therapy

Amiodarone within 4 weeks before screening;

Any other antiarrhythmic agent—including herbal preparations with antiarrhythmic properties—within 1 week before screening.

f) Other serious cardiac conditions

Unstable angina, severe congenital heart disease (except patent foramen ovale), prior prosthetic heart-valve replacement, acute myocarditis or endocarditis, rheumatic valvular disease, or hypertrophic obstructive cardiomyopathy.

g) Limited life expectancy

Any comorbid condition with an anticipated survival of < 1 year.

h) Hepatic impairment

Active hepatitis or clinically significant liver dysfunction (ALT or AST $> 3 \times$ ULN, or total bilirubin $> 3 \times$ ULN).

i) Renal impairment

Estimated glomerular filtration rate $< 40 \text{ mL} \cdot \text{min}^{-1} \cdot 1.73 \text{ m}^{-2}$ (CKD-EPI formula).

(10) Concurrent investigational therapy

Use of any investigational drug or device within 1 month—or five elimination half-lives, whichever is longer—before screening.

(11) Pregnancy or lactation

Pregnant or breastfeeding women, or a positive serum pregnancy test before randomization.

(12) Metabolic, surgical, or pulmonary instability

Uncontrolled hyperthyroidism.

Perioperative cardiothoracic surgery — defined as the interval from 1 week before to 2 weeks after the procedure;

Uncorrected electrolyte imbalance (serum potassium $> 5.5 \text{ mmol/L}$ or $< 3.5 \text{ mmol/L}$; serum magnesium $< 1.5 \text{ mmol/L}$);

Chronic obstructive pulmonary disease with respiratory failure or active, uncontrolled infection.

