1.3.2 Sample- Size Determination

Based on the results of our preliminary exploratory single-arm study evaluating the efficacy of memantine in the treatment of PACs, the 24-hour mean reduction in PACs was 75.4%. Considering the robustness of results from the small-sample trial and potential sampling error, we conservatively estimated a 50% reduction in the 24-hour mean burden of PACs following treatment with memantine, while the placebo group is expected to show a 30% reduction, with a standard deviation of 35%. The dropout rate is assumed to be 15.0%. Using EAST 6.5 software for sample size calculation with a one-sided $\alpha = 0.025$ and a 1:1 allocation ratio between the memantine and placebo groups, a total of 256 participants will be enrolled, providing more than 95% power to detect the pre-specified between-group difference.

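### The NSAT responder rate counts participants without baseline NSAT as failures, and the SAT/AF/AFL count analysis has a baseline fixed at zero by the exclusion criteria (minor)

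*SAP*

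**What the plan says.** **Item g.** In SAP 4.2.2, "an NSAT responder is defined as a participant whose 24-hour mean NSAT burden is reduced by" at least 50% from baseline. The same section states that "All secondary efficacy end points will be evaluated in the FAS", and SAP 2.2 defines the FAS as everyone randomized and dosed. The only arrhythmia required for entry is PACs (Protocol 4.1: "Symptomatic PACs: Documented at screening as" at least 1,000 in 24 hours). No inclusion criterion mentions NSAT. For categorical endpoints, "Participants with missing data will be classified as non-responders". The SAP attaches an absolute difference, a stratified CMH test, a relative risk and an NNT to the responder rate.

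**Item c.** The endpoint is "The change from baseline in the 24-hour mean episode count of SAT, AF, and AFL at Weeks 4, 6, and 8". SAP 4.2.2 fits an ANCOVA with treatment, age and the endpoint's own baseline; for continuous endpoints "analyses will be based exclusively on observed values (observed-cases approach"). SAP 3.1.1 defines change as baseline minus post-baseline. Protocol 4.2, exclusion (1), removes anyone with "AF, AFL, or SAT documented by 12-lead ECG within 6 months before screening or detected on the baseline 72-hour patch-type ambulatory ECG".

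The testing hierarchy in SAP 2.4 contains the PAC responder rate and the change in NSAT burden. It contains neither the NSAT responder rate nor item c.

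**The concern.** A relative-reduction responder definition has meaning only for people who have something to reduce. If part of the FAS has no NSAT at baseline, those participants are failures by construction in both arms. The rate and the NNT then describe a mixture of people who could respond and people who could not, and the reader is not told the proportions.

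For item c, the exclusion criterion removes the variation that a baseline adjustment needs. What remains is a normal-theory comparison of mean follow-up counts. If most participants have none and a few have many, the mean difference and its standard error depend on those few.

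What is at stake is how two supporting endpoints are interpreted. The trial's main conclusion is not in question.

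**Working it through.** **Plan's own figure.** The documents give no design figure for either endpoint. The only one is the primary power of more than 95%. With a difference of 20, an SD of 35 and 108 per arm after 15% dropout, power is 98.7%, which agrees with it.

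**Item g: how a zero baseline is coded.**
1. A participant who goes from 0 to 0 has had no reduction, so the definition is not met.
2. The percent-change formula in SAP 4.2 divides by baseline and is undefined at 0. If that is treated as missing, the categorical rule again gives non-response.
3. Both routes lead to non-response.

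**Item g: effect on the estimates.** Let p1 and p0 be the responder rates among those with baseline NSAT, and z the zero-baseline share, equal in both arms by randomization.
- FAS rates are (1 - z)p1 and (1 - z)p0.
- Risk difference = (1 - z)(p1 - p0). NNT = 1/[(1 - z)(p1 - p0)].
- The relative risk does not change: p1/p0.

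Assumptions: p1 = 50%, p0 = 30%, z = 10, 30 or 40%. None of these is in the documents. Power is from the two-proportion formula with pooled variance, two-sided 0.05, with 128 per arm for the FAS and 128(1 - z) when restricted to baseline above zero.

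No missing data:

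| z | FAS rates | Difference | NNT | Power, FAS | Power, restricted |
|---|---|---|---|---|---|
| 10% | 45% vs 27% | 18 points | 5.6 | 85.5% | 87.8% |
| 30% | 35% vs 21% | 14 points | 7.1 | 70.6% | 78.5% |
| 40% | 30% vs 18% | 12 points | 8.3 | 61.4% | 72.0% |

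The restricted difference is 20 points with NNT 5.0 throughout.

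With the SAP's 15% dropout also counted as non-response (rates multiplied by 0.85), the restricted difference is 17 points (NNT 5.9). In the FAS it is 15.3, 11.9 and 10.2 points (NNT 6.5, 8.4, 9.8). Power is 76.0, 61.0 and 52.6% in the FAS against 78.1, 67.3 and 60.6% restricted. Over assumed rates from 40% vs 20% to 70% vs 50%, the power loss with this dropout is 1.3-4.4 points at z = 10%, 4.3-11.5 at 30% and 5.7-13.5 at 40%.

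**Item c: the model.** With baseline equal to 0 for all, the design matrix (intercept, treatment, age, baseline) has rank 3 of 4. The baseline term drops out, and the treatment difference equals that of a model without it. Change = 0 - follow-up count.

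**Item c: behaviour with sparse counts.** There are 109 observed per arm (128 x 0.85). It is assumed that 3% vs 12% are affected, with 1 plus a negative-binomial number of episodes per 72 hours in those affected. Power over 10,000 runs:

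| Episodes per affected participant | ANCOVA | Stratified rank test | CMH on proportion affected |
|---|---|---|---|
| one each | 74% | 74% | 74% |
| mean 2 | 59% | 73% | 73% |
| mean 3, skewed | 43% | 74% | 74% |
| mean 6, highly skewed | 26% | 73% | 73% |

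With no treatment effect and 3-8% affected, the unadjusted t-test rejects in about 4.4-5.6% of runs with one episode each, 2.8-4.3% at a mean of 2, and roughly 1-3% in the two skewed settings.

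**Item c: illustration (unadjusted).** Suppose 2 memantine and 11 placebo participants each have one episode in 72 hours. The difference is (11/3 - 2/3)/109 = +0.028 episodes per 24 hours (95% CI 0.007 to 0.048, P = 0.010). Now let one of the two memantine participants have 10 episodes. Then (11/3 - (1/3 + 10/3))/109 = 0.000 (-0.063 to 0.063, P = 1.00). The interval is about three times as wide, yet the numbers affected have not changed.

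**The case against.** **The FAS analysis of item g is legitimate.** This stands. Baseline NSAT is fixed before randomization, so the comparison is valid under the null, and an NNT over everyone enrolled is a real quantity. Restriction changes the target population; it does not remove a bias. NSAT in all participants is already covered by the absolute change in burden, which is defined at zero baseline and is in the hierarchy.

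**The sizes are assumed.** This also stands. At z = 10% the power loss is about 2 points, and losses near 10 points need z of 30-40%, which the documents neither support nor exclude. The factor (1 - z) needs no assumed response rate.

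**The item c illustration shows no error.** Correct. Each arm then has 11 episodes, so 0.000 is the right mean difference. A rank test asks a different question, essentially that of item d, so the power columns compare different targets. The example shows only that the mean says little about how many participants were affected.

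**Stronger readings.** A reader might infer that the same data could yield several NNTs, because 0-to-0 could be coded as a response. The definition requires a reduction and missing values are non-responses, so the text supports one coding. A reader might also infer that the constant covariate breaks or biases the ANCOVA; it only drops out. Nor is the ANCOVA conservative in general: it is close to nominal with one episode each and loses size and power only as counts become skewed.

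**Conclusion.** The point holds as a minor improvement. As written, the NSAT responder rate includes as failures any participants who had no NSAT to reduce. This shrinks the risk difference by (1 - z) and inflates the NNT by 1/(1 - z), while the relative risk is unchanged. For z of 10-40% and assumed rates of 50% vs 30%, the NNT is 5.6 to 8.3 instead of 5.0. That zero-baseline participants exist is possible under the entry criteria; their share is unknown.

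For item c, the zero baseline follows from exclusion (1) for every eligible participant. Only someone randomized in error could differ. That the counts are sparse is an inference from the exclusion and the 72-hour windows; no event rate is given. If it is right, the mean difference is fragile and may have little power. It does not inflate false positives.

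A reader might take this as a threat to the trial's conclusions. It is not: both endpoints lie outside the fixed sequence, and items d and e already compare the participants affected.

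**What to change.** **Item g.** Calculate the NSAT responder rate, absolute difference, relative risk and NNT among FAS participants with baseline NSAT burden above zero. State the number with zero baseline in each arm. Report new NSAT at Weeks 4, 6 and 8 separately in those participants. The restriction uses a pre-randomization value, so the randomized comparison is kept.

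**Item c.** Drop the baseline term and summarise descriptively by arm: number affected, and median and maximum episodes among them. Rely on items d and e for between-group comparison. A rank test is not needed, since its simulated power equals that of the test on the proportion affected. The descriptive option also agrees with Protocol 7.3.6, although the SAP takes precedence where the two differ.

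**Cost.** SAP wording only; no new data. The NSAT responder denominator becomes smaller than the FAS, and item c loses its p value.
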